3.1 General Design

In a randomized controlled cross-over design, fourteen adults (7 females, 7 males) with T1D of at least 1-year duration and HbA1c $<9\%$ will undergo three conditions, in a randomized order: 1) high intensity interval training exercise session (HIIT) at 90% peak oxygen consumption (VO_2 peak); 2) moderate intensity exercise session (MICT; 65% VO_2 peak; or 3) a control session (CON; no exercise) (Figure 2).

Subjects will be asked to arrive to the laboratory after an overnight fast (8 hrs) and their usual dose of insulin administered the day prior, with no morning mealtime insulin the day of testing. The lower and higher limit for pre-exercise (i.e. fasted) glucose concentration (i.e. 10 minutes prior to the exercise start time) will be set at 90 and 250 mg/dL, respectively, and the session will be rescheduled if the pre-exercise glucose value is not in range or if hypoglycemia (blood glucose: <70 mg/dL) occurs within an hour of exercise start time. Subjects will also be asked to arrive to testing sessions following a 12 hour fast from caffeine and alcohol and to abstain from physical activity for 24 hours prior to testing. Subjects will complete one electronic contact (phone/email screening) and up to five in-person sessions (enrollment; baseline testing; three conditions [HIIT, MICT, CON]) over the course of 4 weeks

All data collection will be conducted by the Principal Investigator and Research Assistants. All subjects will report to the Applied Physiology Laboratory in [name] for consenting, enrollment, testing, and exercise sessions.

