3.2 Primary Study Outcomes

The primary study outcomes include circulating metabolites that will be measured using an untargeted mass spectrometry-based platform with fasting concentrations of up to 1500 endogenous metabolites related to mitochondrial function, fatty acid oxidation, insulin resistance, and glucose regulation. Targeted metabolomics analysis for acylcarnitines and amino acids will be completed; non-targeted analyses will also be performed as an exploratory analysis, in order to promote the identification of unknown metabolites in addition to the known biology and physiology. Responses will be collected prior to, immediately post, and 1 hr post exercise.

3.2a. Secondary Study Outcomes

Counterregulatory hormones (cortisol, lactate, glucagon) will be evaluated at the same time points. Glucose will be continuously monitored for 48 h post exercise. , and glycemic control through 48 hrs after HIIT, compared to MICT versus a no exercise CON.

3.2b. Tertiary Study Outcomes

Tertiary outcomes will evaluate the influence of biological sex and physiological outcomes (i.e. body composition, lean mass, visceral fat) on the metabolomics profile of these subjects.

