Approximately 8 mL of blood sample (~ 1.5 teaspoons) using an EDTA tube will be taken upon arrival, immediately after exercise, and one-hour post exercise. CON intervention visit will consist of a single blood draw. Circulating metabolites will be measured using an untargeted mass spectrometry-based platform with fasting concentrations of up to 1500 endogenous metabolites related to mitochondrial function, fatty acid oxidation, insulin resistance, and glucose regulation. Analysis will be completed at the Duke Molecular and Physiology Institute Metabolomics Core, directed by [name]. Targeted metabolomics analysis for acylcarnitines and amino acids will be completed; non-targeted analyses will also be performed, in order to promote the identification of unknown metabolites in addition to the known biology and physiology. Counterregulatory hormones (cortisol, lactate, glucagon) and insulin will be analyzed. Samples will be centrifuged immediately upon collection, and aliquots of plasma will be immediately frozen at -80° C for batch analysis. All blood draws will be done in the Applied Physiology Lab by an individual trained in phlebotomy. The current lab group has previously received approval for intravenous blood draws from the antecubital region in several IRB#, to name a few: 16-1991, 15-0543, and 14-0777, with no adverse events reported.

Treatment Regimens: (~20- 30 minutes)

- 1) HIIT Intervention: A 2 minute self-selected warm-up, followed by 10 alternating sets of one minute of pedaling at a resistance corresponding to 90% of VO₂peak and one-minute in active recovery at 50 watts (W). The work completed during each interval will be calculated by multiplying the power output for each participant at 90% VO₂peak by the duration of the interval (60 s). The work completed during each recovery period will be added by multiplying the power output (50 W) by the duration of the recovery period (60 s). The work from both bouts will be added together and then multiplied by 10 to calculate the total amount of work that each participant will complete in the HIIT trial.
- 2) MICT Intervention: Subjects will cycle continuously at a workload corresponding to 65% VO₂peak (W) for a pre-calculated length of time (~20-30 minutes), equivalent to the work that will be completed in the HIIT trials.
- 3) CON Intervention: No exercise will be performed. Subjects will arrive to the lab following the same pre-testing guidelines followed for HIIT and MICT trials.

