5.1 Sample Size Determination

The proposed study was powered based on consideration of multiple effect size calculations from a single bout of HIIT vs MICT in young men ($F=0.25-0.99$)(16) on markers of carbohydrate oxidation, glucose, citric acid, and succinate acid. To achieve statistical power of 0.80, with a conservative correlation of 0.5 between repeated outcomes, the estimated sample size required was $N=12$. To account for an 18% dropout/disqualification rate and for equal groups we propose to enroll 14 adults with T1D, with an equal sample of men ($n=7$) and women ($n=7$).

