5.2 Statistical Methods

For aim 1, changes in the first principal component, as well as any additional components for which the associated eigenvalue is greater than one, will be evaluated using paired t-tests at the 2-sided 0.05 level. Changes in individual metabolic intermediates will be evaluated using paired t-tests at the 2-sided 0.01 level. Differences in metabolomics and counterregulatory hormones markers between treatment regimens will be evaluated using two-way ANOVAs [regimen (HIIT vs. MICT vs. CON) \times time (base vs. immediate post vs. 1h post)]. Exploratory analysis of the modulatory effects of sex on metabolomics markers will be evaluated using separate regimen-by-sex mixed factorial ANOVAs [regimen \times sex], at each time point.

For aim 2, CGM data will be evaluated as previously recommended; data will be aggregated over the 24hrs; area under the curve data will be compared across trials.(25) Counter-regulatory hormones will be evaluated using a two-way mixed factorial ANOVA. Activity data will be captured to potentially be used as a covariate when collating CGM data.

For aim 3, spearman correlations will be completed to understand associations between metabolomics outcomes and physiological variables (i.e. body fat, lean mass, visceral fat).

6 Safety and Adverse Events

Risks associated with participating in this study are **possible**. In-test monitoring by the research team, who are certified fitness professionals trained in CPR/AED, are in place to ensure the safety of all subjects. Personnel trained in phlebotomy and with radiation exposure training will complete the blood draws and DXA scans, respectively.

In accordance with the Exercise and Sport Science Institutional Review Board Standard Operating Procedures (EXSS-IRB SOP), 3 trained research personnel (for safety purposes per IRB procedures) will perform cardiorespiratory fitness testing. Other precautions include: licensed medical professional (MD, ATC) on call, operational AED, and a land line within 10 feet of the testing in order to make emergency call, if required. Additionally, the lab is located within 500 feet of the University Athletic Training facility. If a cardiovascular event does occur, 911 will be called; UNC Hospitals and Emergency room are in very close proximity to the lab.

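### Section 5.2 uses the pre-session sample as an outcome level and never as a covariate, so the HIIT–MICT comparison is valid but avoidably inefficient, by an amount that depends on the ANOVA term read and on the correlations

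*Combined protocol and SAP*

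**What the plan says.** Section 3.1 describes the design: "In a randomized controlled cross-over design, fourteen adults (7 females, 7 males) with T1D" each undergo HIIT, MICT and CON in random order. For the primary outcome, circulating metabolites, section 3.2 says "Responses will be collected prior to, immediately post, and 1 hr post exercise". Section 4.1 (Metabolomics) says that the blood samples "will be taken upon arrival, immediately after exercise, and one-hour post exercise", but for the control condition that the "CON intervention visit will consist of a single blood draw".

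The between-regimen analysis is in section 5.2: "Differences in metabolomics and counterregulatory hormones markers between treatment regimens will be evaluated using two-way ANOVAs". The factors are regimen (three levels) and "time (base vs. immediate post vs. 1h post". The arrival sample is therefore one of three values of the dependent variable. The possible covariates named in sections 4.1 and 5.2 are estradiol, dietary intake and activity. The outcome's own pre-session value is not among them. Section 5.2 does not say whether the interaction, the regimen main effect or a comparison at one time decides the regimen question.

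Section 5.1 plans the sample size "To achieve statistical power of 0.80, with a conservative correlation of 0.5 between repeated outcomes" and arrives at N=12. It gives one correlation and does not separate samples from the same visit from samples on different visits.

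**The concern.** The regimen cannot affect a sample drawn before the session starts. A three-level ANOVA nevertheless treats that sample as a response, and a HIIT–MICT difference can then appear in two places.

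- **Interaction.** This compares post-minus-base changes between regimens. It subtracts the whole baseline difference, however weakly baseline predicts the post value, and so may add noise.
- **Regimen main effect.** This averages over all three times. A difference d present only at the two post times is diluted to 2d/3.

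Baseline adjustment estimates how much of the baseline difference to remove. At stake is precision for the primary outcome in a trial planned on 12 evaluable people. The HIIT and MICT pre-session samples are already being drawn.

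**Working it through.** **Inputs.** N=12, 14 enrolled, correlation 0.5, power 0.80 and f=0.25 to 0.99 are from section 5.1. Assumptions, because the plan gives no figure: two-sided 0.05 for the ANOVA and the sample size; a true HIIT–MICT difference of 1 SD; within-visit correlation rw from 0.5 to 0.9, with between-visit correlation rb held at 0.5.

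**The plan's own figure.** For the 3×3 regimen × time interaction with f=0.25, the noncentrality is 0.25² × 12 × 9/(1 − 0.5) = 13.5 on 4 and 44 df. Power is 0.807, and 12 is the smallest N that reaches 0.80. A single three-level factor with f=0.40 also gives N=12, so the match does not show which test was powered.

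**Variances at one post time** (units of σ²/n). Let Dp and Db be the within-person HIIT–MICT differences after and before the session.

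- Var(Dp) = Var(Db) = 2(1 − rb) = 1.0 at rb=0.5
- Cov(Dp, Db) = 2(rw − rb), so their correlation is R = (rw − rb)/(1 − rb)
- Interaction contrast: Var(Dp − Db) = 4(1 − rb) − 4(rw − rb)
- Baseline-adjusted: 2(1 − rb)(1 − R²)
- Ratio of the two: 2/(1 + R)

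| rw/rb | R | Interaction | Adjusted | Post only | Ratio |
|---|---|---|---|---|---|
| 0.5/0.5 | 0 | 2.0 | 1.0 | 1.0 | 2.00 |
| 0.7/0.5 | 0.4 | 1.2 | 0.84 | 1.0 | 1.43 |
| 0.8/0.5 | 0.6 | 0.8 | 0.64 | 1.0 | 1.25 |
| 0.9/0.5 | 0.8 | 0.4 | 0.36 | 1.0 | 1.11 |

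Estimating the slope inflates the adjusted variance by 1 + 1/(n − 3). At n=12 this is 1.11, so the ratio of 2.00 becomes 2/1.11 = 1.80. At n=14 it is 1.09, giving 1.83. Simulation gave 1.81 and 1.83. In the last row 1.11/1.11 = 1.0, so the gain is gone.

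**Power at one post time**, n=12, 1 SD (interaction and adjusted simulated, post only from the noncentral t):

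| rw/rb | Interaction | Adjusted | Post only |
|---|---|---|---|
| 0.5/0.5 | 61% | 84% | 88% |
| 0.7/0.5 | 82% | 90% | 88% |
| 0.8/0.5 | 94% | 96% | 88% |
| 0.9/0.5 | >99% | >99% | 88% |

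**Main effect against the adjusted post mean**, with the difference at both post times.

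- Main effect: variance [6(1 − rb) + 12(rw − rb)]/9, multiplied by (3/2)² = 2.25 to undo the dilution
- Mean of the two post differences: variance (1 − rb) + (rw − rb), with covariance 2(rw − rb) with Db
- Adjusted: that variance minus [2(rw − rb)]²/[2(1 − rb)]

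| rw/rb | Main effect, rescaled | Adjusted post mean | Power, main effect | Power, adjusted |
|---|---|---|---|---|
| 0.5/0.5 | 0.333 × 2.25 = 0.75 | 0.5 − 0 = 0.50 | 95% | 98% |
| 0.7/0.5 | 0.600 × 2.25 = 1.35 | 0.7 − 0.16 = 0.54 | 77% | 98% |
| 0.8/0.5 | 0.733 × 2.25 = 1.65 | 0.8 − 0.36 = 0.44 | 69% | 99% |

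The two tests proposed under the fix, like the contrasts they replace, held their Type I error at about 0.05 in simulation.

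**The case against.** The planned ANOVA is valid for HIIT–MICT, and this is a choice between valid analyses. That stands. Several stronger readings are tempting, and the documents do not support them.

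- **That the plan doubles the variance because of its 0.5 correlation.** The factor of 2 holds for any common correlation and only for the post-minus-base contrast at one time. Section 5.1 does not claim that samples about an hour apart correlate no more than samples from visits at least seven days apart. Where they correlate more, the factor is smaller.
- **That the plan always discards information in the baseline.** With equal correlations R=0 and the baseline carries none. The loss comes from subtracting a noisy value, and a plain post-time comparison (88%) beats the adjusted one (84%).
- **That the regimen main effect is useless.** With equal correlations and a difference at both post times it has 95% power, more than the 84% of an adjusted test at one time. It falls behind only as within-visit correlation rises.
- **That the trial is underpowered.** One reading of section 5.1 gives the interaction 80.7% power at N=12, and the 1 SD difference used here is an assumption.

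Two further objections have force. The 61% uses 11 error df; with the ANOVA's pooled error of up to 44 df, under the same equal-correlation model, it is 67%. The gap to 84% narrows but does not close. Aim 1 also compares both exercise regimens with no exercise, and an adjusted HIIT–MICT test does not address that.

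**Conclusion.** The point holds as one of efficiency, not validity. Section 5.2 leaves the deciding term open, and each ANOVA reading has a weak region: the interaction when within-visit correlation is close to between-visit correlation, the main effect when it is well above. The variance penalty of the interaction at one post time runs from 2 (about 1.8 in practice) down to 1.25 at 0.8/0.5, and in power it vanishes at 0.9/0.5. The main effect loses 3, 21 and 30 percentage points against the adjusted post mean at 0.5/0.5, 0.7/0.5 and 0.8/0.5.

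These sizes assume n=12, equal variances, two-sided 0.05 and a 1 SD difference; the main-effect comparison also assumes that the difference is present at both post times. The plan does not give the actual correlations, and they may differ between metabolites. That favours a test that does well across the range over one that depends on a favourable pattern. The change is worth making, but the HIIT–MICT conclusions would not be invalid without it.

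**What to change.** In section 5.2, name the HIIT–MICT comparison explicitly and make it baseline-adjusted: first for the mean of the two post samples, then at each post time. Regress the within-person HIIT–MICT post difference on the within-person pre-session difference and test the intercept. Alternatively, fit a mixed model of the post value on regimen, with the session's pre-session value and the participant's mean pre-session value as covariates.

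The cost is wording, one degree of freedom per test, and a small loss against a post-only test if within-visit correlation is no higher than between-visit (84% against 88% in the example). No new samples are needed.

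Handle comparisons with CON separately. Section 4.1 gives CON a single draw, which cannot fill the three time levels in section 5.2. The two passages must be reconciled, and until then the three-regimen ANOVA should not be relied on.

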Specific Aim 1: To compare the metabolic responses immediately and 1 hr after HIIT compared to MICT matched for total energy expenditure, vs no exercise in 14 adults with T1D. Metabolism will be defined as energy expenditure (via indirect calorimetry), carbohydrate metabolism (tricarboxylic acid intermediates), and fat metabolism (acylcarnitines, respiratory exchange ratio).

Specific Aim 2: To evaluate key counter-regulatory/metabolic hormones (i.e. cortisol, lactate, glucagon, and insulin) during and after HIIT, MICT, and control (CON) sessions and the change in glycemia (using continuous glucose monitoring and glycemic cutpoints [<70 mg/dL, 70 - 180 mg/dL, >180 mg/dL]) for 48 hrs post exercise.

[figure not shown]
Specific Aim 3: To explore the modulatory effect of physiological variables on metabolism, including biological sex, lean body mass and visceral fat (measured from dual energy x-ray absorptiometry). Body fat percentage, lean mass, and visceral fat will be used to characterize the sample; the relationship of these variables with metabolomic intermediates will be assessed.

3 Study Design

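### Section 5.2 plans no HIIT versus MICT contrast for the metabolomics and hormone markers; the three-level ANOVA that it assigns cannot answer that part of Aim 1

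*Combined protocol and SAP*

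**What the plan says.** Specific Aim 1 (section 2) is "To compare the metabolic responses immediately and 1 hr after HIIT compared to MICT matched for total energy expenditure, vs no exercise". It therefore holds two questions: HIIT against work-matched MICT, and exercise against rest. Section 5.1 bases the sample size on "multiple effect size calculations from a single bout of HIIT vs MICT in young men", reported as F from 0.25 to 0.99, and "To achieve statistical power of 0.80, with a conservative correlation of 0.5 between repeated outcomes", which leads to 12 participants and an enrolment of 14.

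For the markers, section 5.2 states: "Differences in metabolomics and counterregulatory hormones markers between treatment regimens will be evaluated using two-way ANOVAs [regimen (HIIT vs. MICT vs. CON"), crossed with base, immediate post and 1 h post. The Study Summary repeats this layout. Neither place names a pairwise contrast, a follow-up test, or a rule for reading the F test. No significance level is given for the ANOVAs.

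Section 5.2 contains other tests:
- paired t-tests of changes in components (0.05) and in individual metabolites (0.01), without saying what is paired;
- exploratory regimen-by-sex ANOVAs at each time point;
- a mixed factorial ANOVA for the hormones under Aim 2, with its factors not named;
- a comparison of CGM area under the curve across trials, with no test named.

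Section 4.1 (Metabolomics) schedules three blood draws at the exercise visits and one at the CON visit.

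**The concern.** The null hypothesis of a regimen or regimen x time term with three levels is that HIIT, MICT and CON all behave alike. It is false as soon as exercise moves a marker away from its resting course, whether or not intensity matters. Section 1.1 expects such movement: it describes metabolic perturbations lasting hours after moderate to high intensity exercise. A significant F would then say only that the three regimens are not all alike.

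At stake is the trial's distinguishing question, whether intensity matters at matched work. With no planned contrast, a significant F could be misread as a HIIT-MICT difference, or pairwise comparisons could be chosen after the results are seen. The single CON draw adds a second difficulty: the ANOVA needs nine regimen-by-time cells per person and the blood schedule fills seven.

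**Working it through.** **Inputs.** From section 5.1: N = 12 (14 enrolled), correlation 0.5, power 0.80, F from 0.25 to 0.99 (read as Cohen's f). Assumed: alpha 0.05 for the ANOVA, unit total variance, equal correlations between all cells, and the size and shape of the exercise effect. The within-person error variance is 1 - 0.5 = 0.5.

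**1. The plan's own N.** For a 3 x 3 within-person interaction, the noncentrality is f² x N x 9 / (1 - 0.5), with 4 and 4(N - 1) df. At f = 0.25 and N = 12 it is 0.0625 x 12 x 9 / 0.5 = 13.5, and power is 0.807; N = 11 gives 0.762. So N = 12 is reproduced. A one-factor, three-level test at f = 0.40 also gives N = 12. Section 5.1 states neither the test nor the f, so the basis of the calculation cannot be identified.

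**2. Omnibus test when HIIT = MICT and CON has three values.** Let the means over time be (0, d, d/2) for both HIIT and MICT and (0, 0, 0) for CON.
- Interaction deviations are -d/6, d/6, 0 for HIIT and for MICT, and d/3, -d/3, 0 for CON. Their squares sum to d²/3, so the noncentrality is N(d²/3)/0.5. At d = 1 and N = 12 it is 8.0 on 4 and 44 df: rejection about 55%.
- Regimen deviations are d/6, d/6 and -d/3. Over three times their squares sum to d²/2, so the noncentrality is N(d²/2)/0.5. At d = 1 and N = 12 it is 12.0 on 2 and 22 df: rejection about 83%.

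Simulation of 20,000 trials per scenario agrees with these formulas:

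| Common exercise effect d | Interaction, N=12 | Regimen, N=12 | Interaction, N=14 | HIIT-MICT contrast |
|---|---|---|---|---|
| 0.5 SD | 16% | 28% | 18% | about 5% |
| 0.8 SD | 36% | 64% | 43% | about 5% |
| 1.0 SD | 55% | 83% | 63% | about 5% |
| 1.5 SD | 92% | 99% | 96% | about 5% |

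If the effect does not decline at 1 h, the figures for d = 1.0 and N = 12 are 69% (interaction) and 98% (regimen).

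**3. One CON draw, as in section 4.1.** Take that draw as the baseline (an assumption). No participant then has all nine cells. In a fit to the seven available cells, with no decline at 1 h:
- the interaction has 2 df, involves only HIIT and MICT, and rejects 4.8 to 6.1% of the time;
- regimen adjusted for time rejects about 5%;
- regimen tested before time is adjusted for rejects 76% (N=12) or 83% (N=14) at d = 1.0.

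The answer depends on a fitting choice that the plan does not state.

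**4. Power of the HIIT-MICT contrast.** The difference between two changes from base involves four measurements, so its variance per person is 4 x 0.5 = 2 and its standard error is √(2/N). For a 1 SD difference the noncentrality is √(N/2): 2.45 at N = 12 and 2.65 at N = 14. Two-sided power is about 61% and 69% at alpha 0.05, and about 31% and 40% at 0.01.

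**The case against.** Four arguments can be made for the plan.

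- **Rejecting is correct.** CON is a legitimate level because Aim 1 includes rest, and an F test that rejects when exercise differs from rest has correctly rejected its own null. Pairwise follow-up of a three-level ANOVA is also routine. This stands. A reader might infer that the plan would credit a HIIT-MICT difference where none exists, but no section says that a significant F will be read that way. What the documents support is that it could be misread and that nothing planned prevents this.
- **Other tests exist.** A reader might infer that the ANOVA is the only between-regimen test in section 5.2. It is not: CGM area under the curve is compared across trials, and sex is examined by regimen. The paired t-tests could even be HIIT-MICT tests of change, although changes over time is the more natural reading. The point is therefore limited to the metabolomics and hormone markers, for which this is the only between-regimen test explicitly assigned.
- **The inflation needs data that section 4.1 does not schedule.** This also stands. The rates in step 2 hold only if CON has three values. With one draw and a time-adjusted fit they fall to about 5%. That does not rescue the ANOVA, which then cannot be run as written.
- **The power claim.** An f of 0.25 made only of exercise versus rest (d = 1.30, HIIT = MICT) gives 0.81 interaction power at N = 12. It is tempting to conclude that the stated power is met with no HIIT-MICT difference. Section 5.1, however, takes its effects from a HIIT-MICT comparison and names no test, so the documents do not support that conclusion.

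**Conclusion.** The concern holds for the metabolomics and hormone markers. The three-level ANOVA assigned to them does not test the HIIT-MICT part of Aim 1, and no contrast that does is planned. With CON measured at all three times and HIIT identical to MICT, the interaction rejects in 16% to 92% of trials and the regimen effect in 28% to 99% at N = 12, for assumed exercise effects of 0.5 to 1.5 SD; a direct contrast stays near 5%. These rates rest on correlation 0.5, equal correlations between cells, alpha 0.05, and an effect halved at 1 h.

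Separately, sections 4.1 and 5.2 conflict on CON sampling, and the result on blood markers is undefined until they are reconciled. The missing HIIT-MICT contrast is a defect under either reading.

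**What to change.** In section 5.2:

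1. Make the deciding HIIT versus MICT analysis a planned within-person contrast: HIIT minus MICT in change from base, at immediate post and at 1 h post, each with an estimate and 95% CI. Do not gate it on the omnibus F. Test it at the levels that 5.2 already uses, 0.05 for components and 0.01 for individual metabolites, and state a level for the hormones, which have none.
2. State that a significant omnibus F alone is not evidence that HIIT and MICT differ.
3. Reconcile the single CON draw in section 4.1 with the three CON time points in section 5.2. Report HIIT-CON and MICT-CON response contrasts only if the reconciled protocol provides CON samples at the post times.

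Items 1 and 2 cost only SAP wording and a few contrast statements; they need no CON draws and no further participants. Item 3 means either extra draws at the CON visit or giving up the response contrasts against rest for blood markers. The statistical price is the lower power shown in step 4, and fewer markers will be reported as differing between regimens.

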Protocol Title: Metabolic, Hormonal, and Physiological Characterization of Isoenergetic High Intensity Interval Training and Moderate Intensity Continuous Training in Adults with Type I Diabetes

Principal Investigator: *[name]
Associate Professor
Director, Applied Physiology Laboratory
Department of Exercise & Sport Science
[name]
[contact]
Email: [contact]*

Co-Investigators: *[name]
Cary C. Boshamer Distinguished Professor of Nutrition & Medicine
Chair, Department of Nutrition*

*M. [name]
Medical Director, Diabetes Care Center Clinical Trials Unit
University of North Carolina*

*[name]
Resident Physician
Department of Family Medicine
University of North Carolina*

Funding Sponsor: *NC Diabetes Research Center
Bowman Gray Center for Medical Education
[name]
[name]*

Version Date: September 17, 2021

NCT Trial: **NCT04664205**

Study Summary

Title	Metabolic, Hormonal, and Physiological Characterization of Isoenergetic High Intensity Interval Training (HIIT) and Moderate Intensity Continuous Training (MICT) in Adults with Type I Diabetes (T1D)
Short Title	HIIT and T1D
Methodology	Randomized Controlled Cross-Over Design
Study Duration	Two years
Study Center(s)	Single site
Objectives	
Aim 1: To compare the metabolic responses immediately and 1 hr after one bout of HIIT compared to MICT matched for total energy expenditure, vs no exercise (control; CON) in 14 adults with T1D.
 
Aim 2: To evaluate key counter-regulatory/metabolic hormones during and after HIIT, MICT, and CON sessions and the change in glycemia (using continuous glucose monitoring and glycemic cutpoints [<70 mg/dL, 70-180 mg/dL, >180 mg/dL]) for 48 hrs post exercise.
 
Aim 3: To explore the modulatory effect of physiological variables on metabolism, including biological sex, lean body mass and visceral fat (measured from dual energy x-ray absorptiometry).

Number of Subjects	14 (7 females, 7 males)
Treatment Regimens	All subjects will undergo three conditions, in a randomized order: 
 1) HIIT 2) MICT 3) CON

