Statistical Methodology	
Aim 1: Principal Component Analysis for metabolomics data; two-way ANOVA [regimen (HIIT vs. MICT vs. CON) \times time (base vs. immediate post vs. 1h post)]
 
Aim 2: Two-way mixed-factorial ANOVA for counterregulatory hormones; Comparison of area under the curve across all trials for CGM, aggregated over 24 hrs
 
Aim 3: Spearman correlations between metabolomic outcome and physiological variables)

Abbreviations and Definition of Terms

Abbreviations and Definitions of Terms	
Abbreviation:	Formal Title:
HIIT	High Intensity Interval Training
MICT	Moderate Intensity Continuous Training
T1D	Type 1 Diabetes
CON	Control (no exercise)
CGM	Continuous Glucose Monitoring
HbA1c	Hemoglobin A1c
VO ₂ peak	Peak Oxygen Consumption
PAR-Q+	Physical Activity Readiness Questionnaire
BMI	Body Mass Index
4C Model	Four Compartment Model
FM	Fat Mass
%fat	Percent Body Fat
LM	Lean Mass
DXA	Dual-energy x-ray Absorptiometry Total Body Scan
BIS	Bioelectrical Impedance Spectroscopy
VT	Ventilatory Threshold
HR	Heart Rate
HR _{max}	Maximal Heart Rate
TIR	Time-in-Range
CHO	Carbohydrate
PRO	Protein
FAT	Fat
NDSR	Nutrient Data System for Research
ELISA	Enzyme-Linked Immunosorbent Assay
MVPA	Moderate-Vigorous Physical Activity
EDTA	Ethylenediaminetetraacetic acid
W	Watts
EXSS-IRB SOP	Exercise and Sport Science Institutional Review Board Standard Operating Procedures
DAIDS	Division of AIDS
AE/SAE	Adverse Event/Serious Adverse Event
UPIRSO	Unanticipated Problems Involving Risks to Subjects or Others
DSMB	Data and Safety Monitoring Board
APL	Applied Physiology Laboratory

1 Introduction

This document is a protocol for a human research study. This study will be conducted according to US and international standards of Good Clinical Practice (FDA Title 21 part 312 and International Conference on Harmonization guidelines), applicable government regulations and Institutional research policies and procedures.

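### The hormone model is specified twice and inconsistently, and the two-way mixed factorial ANOVA named for aim 2 cannot fit regimen by time in this cross-over.

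*Combined protocol and SAP*

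**What the plan says.** The hormone analysis is stated in three places.

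- Section 5.2, aim 2 paragraph: "Counter-regulatory hormones will be evaluated using a two-way mixed factorial ANOVA". No factors are named.
- Study Summary, Statistical Methodology: "Two-way mixed-factorial ANOVA for counterregulatory hormones". Again no factors are named.
- Section 5.2, aim 1 paragraph: "Differences in metabolomics and counterregulatory hormones markers between treatment regimens will be evaluated using two-way ANOVAs", with regimen (three levels) and time (three levels) as the factors. This ANOVA is called neither mixed nor repeated-measures.

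The design facts are clear. The Study Summary says "All subjects will undergo three conditions, in a randomized order", and Section 3.1 calls the trial a cross-over. On sampling, Section 3.2 says "Responses will be collected prior to, immediately post, and 1 hr post exercise", and Section 3.2a adds "Counterregulatory hormones (cortisol, lactate, glucagon) will be evaluated at the same time points".

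The plan names factors for a mixed factorial ANOVA only once, in the aim 1 paragraph: "separate regimen-by-sex mixed factorial ANOVAs", run at each time point. There sex is a genuine between-person factor. That sentence covers metabolomics markers and does not mention hormones.

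The plan states no error term, sphericity correction, or period or sequence term for any of these analyses.

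**The concern.** A mixed factorial ANOVA combines at least one between-person factor with at least one within-person factor. Here regimen and time are both within-person. A two-way version must therefore either treat one of them as between-person, which contradicts the design, or bring in another factor such as sex and drop regimen or time. Specific Aim 2 needs both, since it concerns hormones during and after each of the three sessions.

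Two things are at stake. First, under one possible coding the precision that a 14-person cross-over relies on is lost for the regimen main effect. Second, two different models for one set of outcomes leave the choice open until the data are in hand.

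**Working it through.** **Inputs.** Section 5.1 gives effect sizes of 0.25 to 0.99 (read here as Cohen's f, lower bound used), correlation r = 0.5 between repeated outcomes, power 0.80, a required N of 12 and 14 enrolled. The effect sizes come from carbohydrate oxidation, glucose, citric acid and succinate markers, not hormones. A two-sided 0.05 level is stated only for the principal-component t-tests and is assumed here. Compound symmetry is also assumed.

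**Step 1: the plan's own figure.** For a fully within-person 3 × 3 interaction, λ = f² × N × 9 / (1 − r), with 4 and 4(N − 1) degrees of freedom. At N = 12, λ = 0.0625 × 12 × 9 / 0.5 = 13.5 and power is 0.807; at N = 11 it is 0.762. So N = 12 is reproduced, though other models can also give 12.

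**Step 2: the possible two-way mixed readings.**

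| Between | Within | Consequence |
|---|---|---|
| Regimen | Time | 14 people analysed as 42; wrong error term for regimen |
| Time | Regimen | Contradicts the design; see step 5 |
| Sex | Regimen | Regimen error term right; time omitted |
| Sex | Time | Regimen, the randomized comparison, omitted |

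**Step 3: error term if regimen is entered as between-person.** With total variance 1 and three times per regimen:

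- Correct error mean square (regimen × participant): 1 − r = 0.5.
- Error mean square used (participants within regimen): 1 + 2r = 2.0.
- Ratio: 2.0 / 0.5 = 4, so the standard error is √4 = 2 times too large.
- Over r = 0.3 to 0.7 the ratio runs from 1.6 / 0.7 = 2.3 to 2.4 / 0.3 = 8.

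**Step 4: power for the regimen main effect under that coding.** These are 20,000 simulated trials per setting, with n = 14, f = 0.25 and all nine cells filled.

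| r | Both factors within-person | Regimen as between |
|---|---|---|
| 0.3 | 0.82 | 0.39 |
| 0.5 | 0.93 | 0.24 |
| 0.7 | 0.99 | 0.13 |

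The noncentral F agrees for the correct test at r = 0.5: λ = 0.0625 × 14 × 9 / 0.5 = 15.75, with 2 and 26 degrees of freedom, gives 0.93. Under the null at r = 0.5 the mis-specified test rejects about 0.0002 of the time instead of 0.05.

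The regimen-by-time interaction is hardly affected: its null rejection rate is 0.048 against 0.049 for the correct test (n = 14, r = 0.5). If participant-by-time variance is assumed to be 10% of the total, it becomes conservative, at about 0.02.

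**Step 5: the other readings.**

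- Time as between: no material harm under compound symmetry, but the type I error for regimen is about 0.11 to 0.16 if participant-by-regimen variance is 10 to 20% of the total (assumed).
- Sex as between, regimen within, one time point, n = 14, f = 0.25: λ = 0.0625 × 14 × 3 / 0.5 = 5.25. Power is 0.472 with 24 error degrees of freedom, against 0.476 with 26 when sex is left out. Almost nothing is lost.

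**Step 6: cells that will have data.** Section 4.1 (Metabolomics) gives the CON visit a single blood draw. HIIT 3 + MICT 3 + CON 1 = 7 of the 9 regimen-by-time cells. The full 3 × 3 ANOVA in the aim 1 paragraph cannot be fitted to these data either.

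**The case against.** A reader might infer that the regimen effect will be tested against the wrong error term. The documents do not support that. The factors of the mixed ANOVA are not named, and the aim 1 paragraph also gives the hormones a regimen-by-time ANOVA. Where the plan does name mixed factors, it pairs regimen with sex, which leaves the regimen error term correct. That objection stands, and it makes the power loss conditional.

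The sex reading does not rescue the sentence. The regimen-by-sex analysis is confined to metabolomics markers, and carrying it over to hormones one time point at a time would leave the change over time untested.

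It can also be argued that the sample size shows within-person intent, because N = 12 fits a fully within-person 3 × 3 interaction. This is weak evidence. The interaction in a mixed design with regimen as a three-group factor needs 35 in total, or 36 in equal groups, which is 12 per group. The number 12 therefore does not separate the two.

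The size is also fairly called a worst case. It concerns only the regimen main effect, which averages in the pre-exercise sample. It borrows f = 0.25 from other markers and assumes nine filled cells when there will be seven. The interaction, which carries the question of differing responses over time, is largely spared. All of this stands. Hormones are also secondary outcomes.

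**Conclusion.** Wrong as written: the model named for aim 2 does not fit the design. This is more than missing detail, because every two-way mixed reading either treats a within-person factor as between-person or drops a factor that aim 2 needs, and the same section states a different model for the same hormones.

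The magnitude is conditional. Only if regimen is entered as between-person is its main effect tested against an error term about 4 times too large, with power of 0.24 instead of 0.93 at n = 14 (0.39 to 0.13 instead of 0.82 to 0.99 over r = 0.3 to 0.7). Those figures rest on compound symmetry, complete 3 × 3 data, a 0.05 level and f = 0.25 from non-hormone markers. They show what that coding would cost; they do not predict what the trial will do.

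**What to change.** Replace the hormone statements in both paragraphs of Section 5.2 and in the Study Summary with one model that treats regimen and time as within-person. Either of these would do:

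- A linear mixed model with regimen, time, regimen × time and period as fixed effects, participant and visit within participant as random effects, and small-sample degrees of freedom. With one CON draw, only the seven observed cell means can be estimated, so the interaction and all time contrasts should be limited to HIIT and MICT.
- A two-way repeated-measures ANOVA restricted to HIIT and MICT over the three times. Its interaction test at f = 0.25 and r = 0.5 has λ = 0.0625 × 14 × 6 / 0.5 = 10.5, with 2 and 26 degrees of freedom, and power 0.79 at n = 14 (0.71 at n = 12).

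Add sex as a between-person factor only if that is intended, and say so. State in the same text how the single CON sample will be used, so that Sections 4.1 and 5.2 agree.

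The cost is SAP wording and standard software, with no change to visits or sampling.
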